In 16 participants with BMI 25-34.99 kg/m², treated before and after two meals of the day with T6 dermatomal electrical stimulation (delivered by a TENS unit), we aim to compare baseline measurements of gastric emptying of solids with measurements on day 1 of treatment and after 4 weeks and 3 months of treatment. We also aim to compare baseline measurements of fasting and postprandial gastric volume, satiation, satiety, appetite, and weight with measurements after three months of treatment.

EXPERIMENTAL DESIGN

Overweight or class I obesity participants who are not on metformin and have not been diagnosed with type 2 diabetes mellitus (other than dietary advice for borderline hyperglycemia) will be recruited for the study.

Participants will undergo baseline measurements of height, weight, BMI, pulse, blood pressure, gastric function, satiation, satiety, and incretin hormones, over a period of 3 to 7 days. In an open-label study, all 16 participants will receive 15-minute T6 dermatome cutaneous stimulations with a TENS unit applied immediately before ingestion of two of the main meals of the day (breakfast and evening meal), and 60-minute stimulations applied immediately after ingestion of these meals.

[figure not shown]
Participants will attend the Mayo Clinic Clinical Research Trials Unit during the first day of treatment, within 2 weeks from completion of baseline testing. During this visit (day 1 of treatment), devices will be provided and participants will receive training on self-administering electrical stimulation. Hence, the first set of electrical stimulations will take place at Mayo Clinic. On this day, participants will also undergo a gastric emptying test as a measure of the acute effect of T6 dermatome cutaneous stimulation on gastric emptying.

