- a. Overweight and obese adults (BMI ≥25 kg/m² and ≤34.99 kg/m²) residing within 125 miles of Mayo Clinic in Rochester, MN; these will be otherwise healthy individuals with no unstable psychiatric disease and not currently on treatment for cardiac, pulmonary, gastrointestinal, hepatic, renal, hematological, neurological, or endocrine (other than hyperglycemia on diet) disorders.
- b. Age: 18-65 years
- c. Gender: Men or women. Women of childbearing potential will be using an effective form of contraception, and have negative pregnancy tests within 48 hours of enrollment and before each radiation exposure.
- d. Subjects must have the ability to provide informed consent before any trial-related activities.

Eligible individuals will be asked to avoid taking additional medications and supplements for the duration of the study, unless reviewed and approved by the study team.

Exclusion Criteria

a. Abdominal surgery other than appendectomy, Caesarian section or tubal ligation

- b. Positive history of chronic gastrointestinal diseases, systemic disease that could affect gastrointestinal motility, or use of medications that may alter gastrointestinal motility, appetite or absorption, e.g., Orlistat
- c. Positive history of diabetes mellitus or use of hypoglycemic medications
- d. Positive history of spinal cord injury and/or chronic back pain
- e. Significant untreated psychiatric dysfunction based upon screening with the Hospital Anxiety and Depression Inventory (HAD) (12), a self-administered alcoholism screening test (AUDIT-C) (13), and the Questionnaire on Eating and Weight Patterns (binge eating disorders and bulimia) (14). If such a dysfunction is identified by a HAD score >11 or difficulties with substance or eating disorders, the participant will be excluded and given a referral letter to his/her primary care doctor for further appraisal and follow-up.
- f. Intake of medication, whether prescribed or over the counter (except multivitamins), within 7 days of the study. Exceptions are birth control pill, estrogen replacement therapy, thyroxine replacement therapy, low dose analgesia or anti-inflammatory medications (Acetaminophen and Ibuprofen) and any medication administered for co-morbidities as long as they do not alter gastrointestinal motility including gastric emptying and gastric accommodation.
- g. Subjects may also be excluded from participation for other factors at the discretion of the principal investigator.

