Yes, very much	Would you like to eat something sweet?	No, not at all	average of the four individual scores (satiety + fullness + 100-prospective food consumption + 100-hunger / 4.	
Yes, very much	Would you like to eat something salty?	No, not at all	6. Plasma gastrointestinal hormones (ghrelin, GLP-1 and PYY) by radioimmunoassay measured	
Yes, very much Yes, very much	Would you like to eat something savoury?	No, not at all	at fasting, and 15, 45, and 90 minutes	
	Would you like to eat something fatty?	No. not at all		

postprandially during the NDT. The primary endpoint is the peak postprandial level. CCK levels will not be measured in the current study, since they were non-informative in our prior studies. Total ghrelin will be measured by a radioimmunoassay technique (Linco Research, Inc., St. Charles, MO). The assay uses ¹²⁵I-labeled ghrelin and a ghrelin antiserum to determine the level of total ghrelin in plasma.GLP-1 will be measured as the biologically active GLP-1 (active and total) using a 2-site non-competitive immunoassay based on enzyme-labeled quantification of GLP-1 detected by a fluorogenic substrate. PYY will be measured by radioimmunoassay (Linco Research, Inc., St. Charles, MO). PYY exists in at least 2 molecular forms, 1-36 and 3-36, both of which are physiologically active and are detected by the assay.

7. Self-administered questionnaires assessing affect, exercise performance, attitudes, satisfaction with body image, and eating behavior (12-14,23-26).

Statistical Analysis

Sample size assessment - Sample size assessment is based on the results of primary endpoints in the Mayo Clinic lab. Assuming the intra-individual coefficient of variation (or standard deviation) is similar to the inter-individual variation, we have used the SD_{inter} for estimating the power of the study (n=16, baseline versus post-treatment).

Response	Mean	SD	Predicted detectable effect size (%(absolute #)), n=16 on treatment compared to baseline, paired analysis
Gastric emptying, T _{1/2} min*	121.7	29.8	18.4% (22.4 min)
Fasting gastric volume, ml**	225	65	21.8% (49mL)
Gastric accommodation, ml**	507	100	14.7% (75mL)

Data obtained from *ref. 16 and **ref. 20; predicted detectable effect size is shown with 80% power, α =0.05.

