The sample size of 16 on-treatment relative to baseline will have sufficient power to detect a difference in gastric emptying of 22.4 min, of fasting gastric volume of 49mL, and in gastric accommodation of 75mL.

Statistical Methods

It is anticipated that all primary and secondary endpoints will be normally distributed. We shall use a paired student's t-test to compare study parameters (differences between baseline and on-treatment). An analysis of covariance may be examined using gender and BMI as covariates, since these may significantly affect gastric functions such as satiation, maximum tolerated volume, and gastric emptying.

Interim Analysis

An administrative interim analysis will be completed after 6 subjects have completed at least 4 weeks of treatment. The data will be submitted in a blinded fashion to the study sponsor's statistician while the investigative team remains blinded to the treatments. This interim analysis will be conducted for administrative purposes to provide information about future planning of other research activities. The

conduct of this study will not be altered and all planned research activities will proceed until the completion of the targeted 16 subjects.

Primary endpoints

- 1. Body weight change from baseline
- 2. Gastric emptying $T_{1/2}$ after day 1 treatment
- 3. Gastric emptying $T_{1/2}$ after 3 months treatment

Secondary endpoints

- 1. Fasting gastric volume
- 2. Postprandial gastric volume or accommodation volume
- 3. Gastric emptying % at 1 hour in day 1 and end of three months of treatment
- 4. Satiation: volume to fullness (grade 3) and maximum tolerated volume (grade 5)
- 5. Satiety: kcal intake at buffet meal
- 6. Appetite score during satiety meal test and at weekly intervals (at home)
- 7. Plasma ghrelin, GLP-1 and PYY fasting
- 8. Peak postprandial plasma ghrelin, GLP-1 and PYY fasting

Anticipated Results and Significance

We anticipate greater weight loss with active treatment with dermatomal stimulation compared to baseline. The sample size is not sufficient to appraise twice versus once daily treatment. However, the data will be tabulated for descriptive analysis. The physiological measurements will provide information about the potential mechanisms involved in any beneficial effects on weight and appetite.

Potential Pitfalls, Precautions Taken, and Alternative Strategies

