- a. Feasibility Given our 500-person database with baseline quantitative traits and genotype, we are confident we will recruit sufficient numbers of participants for these studies that involve mainly noninvasive tests.
- b. The pilot study is intended to document feasibility to recruit and retain subjects in such a 12 to 14-week, hypothesis-generating treatment trial, and to appraise the weight loss achieved in order to characterize the coefficient of variation for planning the sample size of a future hypothesis testing trial.
- c. Exploratory analyses will be performed using the other quantitative traits which are all measured in these studies to assess physiological parameters that may be relevant to any beneficial effects of the treatment in these overweight or class I obese subjects.
- d. In order to develop pre-specified monitoring and analysis plans, we shall establish a DATA SAFETY MONITORING PLAN which will involve review by experts independent of the study, using a team comprised of researchers with track records in biostatistics and clinical trials and expertise in the quantitative biomarker

Device Safety: Designation of Non-Significant Risk

Based on the FDA guidance on Significant Risk and Nonsignificant Risk Medical Device Studies (27), the proposed study does not meet the definition for a significant risk (SR) device study and hence is a non-significant risk (NSR) clinical study.

Moreover, the Elira TENS device is regarded as an NSR device on the following basis:

- It is not implantable
- It does not support or sustain human life
- It is not for use of substantial importance in diagnosing, curing, mitigating or treating a disease (no claims related to obesity have been made by the manufacturer)
- It does not present a potential for serious risk to the health, safety or welfare of the participant

It is important to note that the Elira TENS device is essentially similar to commerciallyavailable, over-the-counter TENS units that can be purchased at local pharmacies and are commonly utilized for self-administered therapy.

Lastly, participants will keep a diary that will serve as a tool for evaluating risk/discomfort potentially associated with the use of the Elira TENS unit. Nausea, dyspepsia and local discomfort on anterior abdominal wall (treatment site) may occur with over-stimulation.

REFERENCES

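### Eligibility sets a BMI range but no weight-stability condition, although body weight change is the first-listed primary endpoint of a single-arm before-after study; the exclusion for appetite and absorption drugs has no time window

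*Combined protocol and SAP*

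**What the plan says.** **Entry.** Inclusion Criteria a admits adults with BMI 25-34.99 who are otherwise healthy. No criterion concerns weight history, recent loss or gain, or participation in a weight-loss programme.

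**Drugs.** Exclusion b opens with a positive history of certain diseases and closes with "use of medications that may alter gastrointestinal motility, appetite or absorption, e.g., Orlistat". It states no period. Exclusion c bars hypoglycemic drugs, also without a period. Exclusion f bars "Intake of medication, whether prescribed or over the counter (except multivitamins), within 7 days of the study", with listed exceptions. Exclusion g leaves other exclusions to the principal investigator and names no weight rule.

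**Design and analysis.** Experimental Design: "In an open-label study, all 16 participants will receive 15-minute T6 dermatome cutaneous stimulations". Baseline testing takes 3 to 7 days, and day 1 of treatment follows within 2 weeks. Weekly home weights are kept only during treatment. The first of three primary endpoints is "Body weight change from baseline". Statistical Methods: "We shall use a paired student's t-test to compare study parameters (differences between baseline and on-treatment"). An analysis of covariance on gender and BMI is optional.

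**Use of the result.** Potential Pitfalls, item b, gives feasibility of recruitment and retention as a purpose of the pilot, and also "to appraise the weight loss achieved in order to characterize the coefficient of variation for planning the sample size of a future" trial.

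**Diet.** Recommended Diet encourages 1200 kcal (women) or 1400 kcal (men) for everyone, with dietitian education at enrollment and daily food diaries.

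**The concern.** In a before-after comparison without a control arm, nothing cancels a trend that was already running. A volunteer midway through a diet programme, or regaining after one, meets every written criterion, and the change on study then mixes that trend with whatever stimulation and the study diet do. Continuing loss makes the treatment look better; regain hides an effect. Because such trends differ between people, they also add to the spread of weight change, which the pilot is meant to describe for the next trial.

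The plan has no later step that would repair this. Three to seven days is too short to show a trend, no serial weights are taken before treatment, and gender and BMI are not measures of prior trend.

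The drug criteria leave a second, less certain route. If b means current use only, the only dated protection against someone who has recently stopped a weight-loss drug is the 7 days in f.

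**Working it through.** **1. The plan's own figures.** The sample size table states that the "predicted detectable effect size is shown with 80% power, α =0.05". A paired t-test with n = 16, two-sided α = 0.05 and 80% power detects 0.7495 SD:

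- Gastric emptying T½: 0.7495 × 29.8 = 22.3 min (stated 22.4).
- Fasting gastric volume: 0.7495 × 65 = 48.7 mL (stated 49).
- Gastric accommodation: 0.7495 × 100 = 75.0 mL (stated 75).

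These reproduce and are not in dispute. The table has no row for body weight, so the documents give neither an SD of weight change nor a target difference. Everything below rests on assumptions.

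**2. Assumed inputs.** Drift r = 0.25 to 0.5 kg/week; 12 weeks; 4 of 16 participants (p = 0.25), all in the same direction; SD of change 3 kg among weight-stable participants; the study diet adds to the prior trend and does not replace it.

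**3. Shift in the mean.**
- Drift per affected participant: L = 12r = 3 to 6 kg.
- One affected: L/16 = 0.19 to 0.38 kg.
- Four affected: 4L/16 = 0.75 to 1.5 kg.
- For scale, the standard error of the mean is 3/√16 = 0.75 kg.

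**4. Variance of weight change.** Mixture variance = 9 + p(1 − p)L².
- Four affected, L = 3: 9 + 0.1875 × 9 = 10.69; ratio 1.19; SD 3.27 kg.
- Four affected, L = 6: 9 + 0.1875 × 36 = 15.75; ratio 1.75; SD 3.97 kg.
- One affected (p(1 − p) = 0.0586): ratios 1.06 and 1.23.
- Two losing and two regaining equally: mean shift 0; variance 9 + 0.25L² = 11.25 to 18; ratios 1.25 to 2.0.

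**5. Coefficient of variation, the quantity the plan names.** CV = SD/mean. Assume a mean loss of 3 or 5 kg among stable participants.

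| Assumed mean loss | Without drift | Four also losing, L = 3 | Four also losing, L = 6 |
|---|---|---|---|
| 3 kg | 3/3 = 1.00 | 3.27/3.75 = 0.87 | 3.97/4.5 = 0.88 |
| 5 kg | 3/5 = 0.60 | 3.27/5.75 = 0.57 | 3.97/6.5 = 0.61 |

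CV² changes by about −24% and −22% in the first row, and −10% and +4% in the second. If the four regain instead, the CV rises: with a 3 kg mean loss and L = 3, 3.27/2.25 = 1.45.

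**6. Masking by regain.** At SD 3 kg, a true mean loss of 2.25 kg (0.75 SD) has 80% power. A mean regain of 0.75 kg leaves 1.5 kg (0.5 SD), and power falls to about 46% by the noncentral t, with the SD held at 3 kg.

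**7. Reading exclusion b.** If its opening words about history govern the whole sentence, any past use of an appetite or absorption drug excludes. If they govern only the diseases, the drug clause refers to use without saying when, and may mean current use. Exclusion f does not settle this, because a volunteer must pass both b and f.

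**The case against.** Several counter-arguments have force.

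- **Drugs.** A reader might infer from f that someone who stopped a weight-loss drug 8 days earlier can certainly enter. The text does not support that: b applies separately and may bar any past user. What stands is that b has no window and can be read two ways. The gap for people already dieting or losing weight is open under either reading.
- **Drift counted in full.** A reader might infer that every kilogram of prior trend appears in the endpoint. That is not shown. Someone already dieting moves to the study diet, which may replace the earlier deficit. The 0.75-1.5 kg is conditional on its not doing so.
- **The next trial.** A reader might infer that the next trial must grow by 19-75%. That follows only if it is sized on the SD at a fixed target difference. The plan speaks of the coefficient of variation, which can move either way.
- **Assumed inputs.** Prevalence, drift rate and SD are not in the documents, and drift in mixed directions can leave the mean unchanged. With one affected participant the shift is at most half a standard error.
- **Pilot status.** The study is described as hypothesis-generating, and the other two primary endpoints are gastric emptying, one of them on day 1, where months of weight drift matter little. This lowers the weight of the point; it does not remove it for the first-listed endpoint.
- **Investigator discretion.** Exclusion g permits exclusion but names no weight rule, so consistent use cannot be presumed.

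**Conclusion.** The point holds as a cheap improvement. No condition on recent weight change or current dieting guards a primary endpoint that is measured against each participant's own baseline without a control, and the planned baseline and analysis cannot detect or remove a prior trend. Exclusion b lacks a time window and is ambiguous.

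The size is unknown from the documents. Under the stated assumptions (4 of 16, same direction, 0.25-0.5 kg/week for 12 weeks, not replaced by the study diet, 3 kg SD when stable), the mean moves by 0.75-1.5 kg and the variance rises by about 19-75%. The direction of bias cannot be predicted, and neither can the direction of change in the coefficient of variation.

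A reader might also infer that a stability rule would make weight loss attributable to stimulation. It would not: all participants are advised the 1200/1400 kcal diet, and there is no diet-only arm.

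**What to change.** Add one exclusion: self-reported weight change above a stated threshold (for example more than 3 kg), or participation in a structured weight-loss programme, within a stated period (for example 3 months) before baseline. The threshold and period are illustrative and are the sponsor's to set; the documents do not supply them.

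In exclusion b, either state a matching look-back for anti-obesity and appetite-altering drugs, or say plainly that any past use excludes. The 7 days in f can stay for other medicines.

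The cost is one criterion, one screening question and a clarified sentence, with no new procedure. Somewhat fewer volunteers will be eligible. The allowance of up to 36 for 16 completers must absorb this along with dropouts, for which the plan gives no rate. The gain is less bias and variance from prior trends; confounding with the study diet remains.

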T6 dermatomal stimulation will be achieved by utilizing an Elira TENS device (Elira Therapeutics, Inc., St. Louis, MO), following the company's protocol. The Elira device provides a broad range of options for stimulation parameters. In particular, pulse width is programmable from 25 μ sec to 400 μ sec, pulse amplitude from 1 mA to 45 mA, pulse frequency from 1 Hz to 200 Hz, session duration from 5 min to 60 min, and number of sessions per day from 0 to 8 sessions.

- Participants will undergo four stimulation sessions per day (daily for at least 3 months) distributed around 2 meals (breakfast and dinner) as follows: A 15-minute pre-prandial session (starting 15 minutes before the meal) and a 60-minute post-prandial session (starting immediately after the meal), during which the participant can walk around and continue to perform regular activities as desired, with the exception of driving and operating machinery
- The stimulation parameters will be: 200 µsec pulse width at 20 Hz with a goal amplitude range of 18-20 mA (depending on the subject's pain threshold). Participants will be instructed to begin each stimulation at 0 mA and increase as tolerated (within 5 minutes) to achieve the 18-20 mA goal.

Clinical trial stimulation will be limited to an accumulated maximum of 150 Joules per day, with a maximum of 0.001 Joules (1 mJ) per pulse. For example, two 15-minute and two 60-minute stimulation sessions at 200 µsec pulse width, 20 Hz and 25 mA deliver an accumulated 40.5 Joules per day, with only 0.23 mJ per pulse, allowing for upward titration as needed. The principal investigator may increase or decrease any of the stimulation parameters at his discretion up to the maximum 150 Joules daily limit.

Blood Samples

[figure not shown]
Fasting, 15, 45, and 90 minute post-prandial blood samples will be collected at the baseline and treatment conclusion visits, and will be stored at -70°C for assay analysis of plasma gastrointestinal hormone levels as well as storing a blood-based DNA sample for possible future genetic testing. Fasting blood glucose will be measured at one of the baseline visits using a glucometer (CRTU nurses).

Quantitative Traits

On different days, participants will attend Mayo Clinic Clinical Research Trials Unit at a prescheduled time after an 8-hour fasting period, and the following validated quantitative traits will be measured.

1. Gastric emptying (GE) of solids by scintigraphy: Scans will be obtained immediately after consumption of test meal and then every 15minutes for the first hour, every 30 minutes for the second hour and then at the 3 and 4 hour timepoints. The primary endpoint is gastric half-emptying time (GE $T_{1/2}$), and the secondary endpoints are proportions emptied at 2 and 4 hours (15). The normal range for GE $T_{1/2}$ is based on 10th and 90th percentiles in healthy volunteers, based on gender (16). In general, GE of liquids is noncontributory in the context of upper gastrointestinal symptoms (17). In order to reduce radiation burden (needing two isotopes to assess both liquid and solid emptying), we will study exclusively GE of solids.

Figure 5

2. Fasting and postprandial gastric volume (GV) by single photon emission computed tomography (SPECT), developed and validated (including performance characteristics) in our lab [Figure 5 (18-20)].

3. Satiation by Ensure® nutrient drink test (1kcal/mL, 11% fat, 73% carbohydrate, 16% protein) with ingestion at a rate of 120

mL every 4 minutes equivalent to a constant rate of 30ml/minute to measure volume to fullness (VTF) and maximum tolerated volume (MTV) (21). Briefly, participants record their sensations of fullness using a numerical scale from 0 to 5, with level 0 being no symptoms, level 3

corresponding to fullness sensation after a typical meal ("volume to fullness"), and level 5 corresponding to the MTV (maximum or unbearable fullness/satiation). Nutrient intake is stopped when subjects reach the score of 5. Postprandial symptoms of fullness, nausea, bloating, and pain are measured 30 minutes after the meal using 100mm horizontal visual analog scales (VAS), with the words "none" and "worst ever" anchored at each end.

4. Satiety- Buffet Meal (for assessment of kcal intake as a measure of appetite) by ad-

libitum buffet meal to measure total caloric intake and macronutrient distribution in the chosen food (15). Five hours after ingesting 300mL liquid nutrient (Ensure®) as part of the SPECT gastric volume study, participants will be invited to eat, during a 30-minute period, a standard ad libitum meal that includes five cheese lasagna (Stouffers®, Nestle USA, Inc., Solon, OH [nutritional analysis of each 304g box: 340kcal (19g protein ((23% of energy)), 41g carbohydrate ((48% of energy)), and 11g fat ((29% of energy))]); vanilla pudding (Jell-O®, Kraft Foods North America, Tarrytown, NY [nutritional analysis of each 110-g carton: 110 kcal (1g protein ((4% of energy)), 23g carbohydrate ((84% of energy)), and 1.5g fat ((12% of energy))]); and skim milk (Kemps Select, Kemps LLC®, St. Paul, MN [nutritional analysis of each 236mL carton: 90kcal (9g protein ((40% of energy)), 13g carbohydrate ((60% of energy)), and 0g fat))]). The total amount (grams and kilocalories) of food consumed and the kilocalories of each macronutrient at the ad libitum meal are analyzed by the study dietitian using validated methods.

Participants will be subdivided into "excessive eaters" [the top tertile (1176 kcal) as defined in a prior study of 264 overweight or obese participants] and the bottom 2 tertiles, defining non-excessive intake among overweight or obese participants.

5. Ratings of appetite will be measured every 30 minutes between the time of ingestion of standard liquid breakfast and the start of the ad libitum meal. Ratings for appetite (satiety, fullness, hunger and prospective food consumption), thirst, wellbeing and nausea will be recorded using VAS, as described by Flint et al. (22). VAS, 100mm in length with words anchored at each end expressing the most positive and the most negative ratings, will be used to assess hunger, satiety, fullness, prospective food consumption, desire to eat something fatty, salty, sweet or savory, and the palatability (5 questions) of the test meal (Figure 6).

l am not hungry at all	How hungry do you feel?	I have never been more hung	Good Visual appeal Bad Bad	
l am completely empty	How satisfied do you feel?	l cannot eat another bite	Good Taste Bad Good Aftertaste	
Not at all full	How full do you feel?	Totally full	Much None Palatability Good Bad	
Nothing at all	How much do you think you can eat?	A lot	Overall appetite score will be calculated as the	
Yes, very much	Would you like to eat something sweet?	No, not at all	average of the four individual scores (satiety + fullness + 100-prospective food consumption + 100-hunger / 4.	
Yes, very much	Would you like to eat something salty?	No, not at all	6. Plasma gastrointestinal hormones (ghrelin, GLP-1 and PYY) by radioimmunoassay measured	
Yes, very much Yes, very much	Would you like to eat something savoury?	No, not at all	at fasting, and 15, 45, and 90 minutes	
	Would you like to eat something fatty?	No. not at all		

postprandially during the NDT. The primary endpoint is the peak postprandial level. CCK levels will not be measured in the current study, since they were non-informative in our prior studies. Total ghrelin will be measured by a radioimmunoassay technique (Linco Research, Inc., St. Charles, MO). The assay uses ¹²⁵I-labeled ghrelin and a ghrelin antiserum to determine the level of total ghrelin in plasma.GLP-1 will be measured as the biologically active GLP-1 (active and total) using a 2-site non-competitive immunoassay based on enzyme-labeled quantification of GLP-1 detected by a fluorogenic substrate. PYY will be measured by radioimmunoassay (Linco Research, Inc., St. Charles, MO). PYY exists in at least 2 molecular forms, 1-36 and 3-36, both of which are physiologically active and are detected by the assay.

7. Self-administered questionnaires assessing affect, exercise performance, attitudes, satisfaction with body image, and eating behavior (12-14,23-26).

Statistical Analysis

Sample size assessment - Sample size assessment is based on the results of primary endpoints in the Mayo Clinic lab. Assuming the intra-individual coefficient of variation (or standard deviation) is similar to the inter-individual variation, we have used the SD_{inter} for estimating the power of the study (n=16, baseline versus post-treatment).

Response	Mean	SD	Predicted detectable effect size (%(absolute #)), n=16 on treatment compared to baseline, paired analysis
Gastric emptying, T _{1/2} min*	121.7	29.8	18.4% (22.4 min)
Fasting gastric volume, ml**	225	65	21.8% (49mL)
Gastric accommodation, ml**	507	100	14.7% (75mL)

Data obtained from *ref. 16 and **ref. 20; predicted detectable effect size is shown with 80% power, α =0.05.

The sample size of 16 on-treatment relative to baseline will have sufficient power to detect a difference in gastric emptying of 22.4 min, of fasting gastric volume of 49mL, and in gastric accommodation of 75mL.

Statistical Methods

It is anticipated that all primary and secondary endpoints will be normally distributed. We shall use a paired student's t-test to compare study parameters (differences between baseline and on-treatment). An analysis of covariance may be examined using gender and BMI as covariates, since these may significantly affect gastric functions such as satiation, maximum tolerated volume, and gastric emptying.

Interim Analysis

An administrative interim analysis will be completed after 6 subjects have completed at least 4 weeks of treatment. The data will be submitted in a blinded fashion to the study sponsor's statistician while the investigative team remains blinded to the treatments. This interim analysis will be conducted for administrative purposes to provide information about future planning of other research activities. The

conduct of this study will not be altered and all planned research activities will proceed until the completion of the targeted 16 subjects.

Primary endpoints

- 1. Body weight change from baseline
- 2. Gastric emptying $T_{1/2}$ after day 1 treatment
- 3. Gastric emptying $T_{1/2}$ after 3 months treatment

Secondary endpoints

- 1. Fasting gastric volume
- 2. Postprandial gastric volume or accommodation volume
- 3. Gastric emptying % at 1 hour in day 1 and end of three months of treatment
- 4. Satiation: volume to fullness (grade 3) and maximum tolerated volume (grade 5)
- 5. Satiety: kcal intake at buffet meal
- 6. Appetite score during satiety meal test and at weekly intervals (at home)
- 7. Plasma ghrelin, GLP-1 and PYY fasting
- 8. Peak postprandial plasma ghrelin, GLP-1 and PYY fasting

Anticipated Results and Significance

We anticipate greater weight loss with active treatment with dermatomal stimulation compared to baseline. The sample size is not sufficient to appraise twice versus once daily treatment. However, the data will be tabulated for descriptive analysis. The physiological measurements will provide information about the potential mechanisms involved in any beneficial effects on weight and appetite.

Potential Pitfalls, Precautions Taken, and Alternative Strategies

- a. Feasibility Given our 500-person database with baseline quantitative traits and genotype, we are confident we will recruit sufficient numbers of participants for these studies that involve mainly noninvasive tests.
- b. The pilot study is intended to document feasibility to recruit and retain subjects in such a 12 to 14-week, hypothesis-generating treatment trial, and to appraise the weight loss achieved in order to characterize the coefficient of variation for planning the sample size of a future hypothesis testing trial.
- c. Exploratory analyses will be performed using the other quantitative traits which are all measured in these studies to assess physiological parameters that may be relevant to any beneficial effects of the treatment in these overweight or class I obese subjects.
- d. In order to develop pre-specified monitoring and analysis plans, we shall establish a DATA SAFETY MONITORING PLAN which will involve review by experts independent of the study, using a team comprised of researchers with track records in biostatistics and clinical trials and expertise in the quantitative biomarker

Device Safety: Designation of Non-Significant Risk

Based on the FDA guidance on Significant Risk and Nonsignificant Risk Medical Device Studies (27), the proposed study does not meet the definition for a significant risk (SR) device study and hence is a non-significant risk (NSR) clinical study.

Moreover, the Elira TENS device is regarded as an NSR device on the following basis:

- It is not implantable
- It does not support or sustain human life
- It is not for use of substantial importance in diagnosing, curing, mitigating or treating a disease (no claims related to obesity have been made by the manufacturer)
- It does not present a potential for serious risk to the health, safety or welfare of the participant

It is important to note that the Elira TENS device is essentially similar to commerciallyavailable, over-the-counter TENS units that can be purchased at local pharmacies and are commonly utilized for self-administered therapy.

Lastly, participants will keep a diary that will serve as a tool for evaluating risk/discomfort potentially associated with the use of the Elira TENS unit. Nausea, dyspepsia and local discomfort on anterior abdominal wall (treatment site) may occur with over-stimulation.

REFERENCES

